7.1. Disposition of Participants and Withdrawals

Since this is a long-term study in a patient population that is elderly with multiple possible comorbidities, some participant withdrawal will occur. Efforts will be taken to obtain information on participants who are initially categorized as lost to follow-up. From the randomized population, the disposition of participants withdrawing from each treatment arm will be summarized and compared.

Participant disposition will include tabulations of the number of overall participants who screen failed for blinded treatment period. The following will be summarized by randomized treatment group and overall:

- Number of participants who enrolled/randomized,
- Number and percentage of participants in each analysis set,
- Number and percentage of participants who completed the study, and
- Number and percentage of participants who discontinued from the study, including the reason for study discontinuation.

The percentage of participants will be based on the ITT analysis set. All disposition results will be presented in a data listing.

7.2. Protocol Violations and Deviations

The severity (important/non-important) will be classified using the following definitions as per Premier Research standard operating procedures (SOPs). A protocol deviation is any noncompliance with the clinical trial protocol or International Council for Harmonization of Technical Requirements for Pharmaceuticals for Human Use (ICH) E6 (R2) Good Clinical Practice (GCP) requirements.

Protocol deviations will be tracked, recorded, and reviewed prior to database lock, following the Protocol Deviation Guidance Plan for this study.

Potentially important deviations will be reviewed by the Sponsor and Premier to determine the final classification. Protocol deviations which are deemed to be “Important” and “Non-Evaluable” (i.e., a deviation that has a potential impact on the efficacy analysis), will be classified into a separate category.

The protocol deviation categories will be:

- Inclusion Criteria
- Exclusion Criteria
- Study Drug
- Assessment – Safety
- Assessment – Efficacy
- Lab/Endpoint Data
- Visit Window
- Informed Consent
- Prohibited Concomitant Medication
- Overdose/Misuse
- Other

The number and proportion of participants with important protocol violations/deviations will be tabulated by category/type and treatment group in the safety analysis set. These protocol violations/deviations will also be presented in a participant listing by randomized treatment.

7.3. Demographics and Other Baseline Characteristics

All participant demographics and other baseline characteristics will be summarized by randomized treatment group using the ITT analysis set. Demographic and other baseline characteristics will also be summarized for the safety analysis set if it is different from the ITT analysis set.

Demographic and baseline characteristics [age, sex (including child-bearing potential for women), methods of contraception, race, ethnicity, weight, height, body mass index (BMI), and education level] will be summarized using the descriptive statistics. Height and weight will be calculated at screening and then the BMI will be calculated at screening.

Additionally, baseline characteristics including AD family history, Covid-19 infection and vaccination history results, and Apolipoprotein E (ApoE) genotyping will be summarized.

The number and percent of participants reporting medical history, grouped by MedDRA system organ class and preferred term, will be tabulated by randomized treatment group. All medical history data will be presented in a data listing.

Prior medications will be summarized descriptively by treatment group using the number and percentage of participants by Anatomical Therapeutic Chemical class (ATC level 2) and preferred term (ATC level 4). All “Cognitive enhancers” defined by verbatim terms: donepezil (Aricept, Adlarity), galantamine (Razadyne, Reminyl), rivastigmine (Exelon) and memantine (Namenda, Ebixa, Nemdatine) will be summarized separately. All prior medication data will be listed. The cognitive enhancers will be flagged in the prior medication listing.

For the continuous variables, the number of non-missing values and the mean, standard deviation, minimum, median, and maximum will be tabulated.

For the categorical variables, the count and percentage of each value will be tabulated.

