2.3. Study Population

The study population is comprised of approximately 800 male or female participants between the ages of 50 and 87 with mild-to-moderate AD dementia. Participants are enrolled (randomized) from approximately 77 clinical sites in the U.S., Canada and Australia.

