6.1.8. Data Adjustments/Handling/Conventions

All collected data will be presented in listings or Clinical Data Interchange Standards Consortium (CDISC) datasets. Analysis results will be presented and summarized in either tables and/or figures. Data not participant to analysis according to this plan will not appear in any tables or graphs but will be included in the data listings.

All p-values will be displayed in four decimals and rounded using standard scientific notation (e.g., 0.XXXX). If a *p-value* less than 0.0001 occurs, it will be shown in tables as < 0.0001.

The version 24.0 of the Medical Dictionary for Regulatory Activities (MedDRA) will be used to classify all AEs by system organ class (SOC) and preferred term (PT).

Prior and concomitant medications will be classified using Anatomical Therapeutic Chemical class (ATC level 2) and preferred term (ATC level 4) from World Health Organization Drug Dictionary (WHO-DD), WHODrug Global B3 version March2021.

Medications that start before the first dose of study drug are considered prior medications whether or not they were stopped prior to the first dose of study drug. Any medication continuing or starting on or after the first dose of study drug will be considered as concomitant. If a medication starts prior to the first dose of study drug and continues after the first dose of study drug, the medication will be considered as both prior and concomitant.

Adverse events or medications with entirely missing start dates will be classified as treatment-emergent or concomitant, as appropriate.

For partial AE or medication start dates: (a) if only the day is missing, and the month and year match the first dose date and the end date is on or after the first dose date, or AE/medication is ongoing, then the date is assigned the first dose date thus the event/medication will be considered as treatment-emergent/concomitant; if the month and/or year do not match the first dose date or the end date is prior to the first dose date, then the day is assigned the first day of the month (01); (b) if month or the day and month are missing, and the year matches the first dose date and the end date is on or after the first dose date, or AE/medication is ongoing, then the date is assigned the first dose date; if the year does not match the first dose date or the end date is prior to the first dose date, then the day/month are assigned the first day of the year (01JAN).

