8.4. Subgroup Analyses of Efficacy Variables

The co-primary endpoints and iADRS will be analyzed by baseline severity, with subgroups defined as screening MMSE ≥ 21 and ≤ 27 versus MMSE < 21 . An additional subgroup analysis for the co-primary endpoints and the iADRS will use screening MMSE ≥ 20 and ≤ 27 versus

MMSE < 20. For these analyses, an MMRM model as previously described will be used, except that the model will have additional fixed effects for subgroup and its two-way interactions with treatment and Visit, and the 3-way subgroup-by-treatment-by-Visit interaction; and, baseline scores for the endpoint being analyzed and baseline MMSE and their interactions with Visit will be removed from the model due to their possible confounding with subgroup. Specifically, the analysis will include the categorical, fixed effects of treatment group, subgroup, pooled site, and Visit, along with the two-way interactions of treatment group with Visit and subgroup with Visit, and the three-way treatment group, subgroup, Visit interaction.

Similar models will be used to analyze subgroups by age (defined as < 65, 65-74 or ≥ 75), sex (defined as male or female), ethnicity (categories defined per FDA Guidance), ApoE4 genotype (defined as APOE4 non-carrier, carrier or homozygous) and medication use (cognitive enhancers, defined as yes or no).

There will be two additional subgroup analyses for the NPI-10. The first will include participants with a baseline NPI-10 score ≥ 2. The second will analyze the agitation/aggression domain scores in participants with a non-zero baseline score in that domain.

Note that there will be two sets of results for the mild subgroup. In section 8.2 the mild subgroup analyses are conducted by applying the primary analysis model to the ITT-mild analysis set. Those analyses are the primary means of drawing inference for the mild subgroup. The subgroup analyses described here for the mild / moderate subgroups are the primary means of drawing inference for differential efficacy between the subgroups. The analyses specified in section 8.2 are the primary means of understanding efficacy within the mild subgroup because that approach allows for including the same model as other secondary and primary endpoints.

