9.6. Concomitant Medications

Concomitant medications will be summarized descriptively by treatment group using the number and percentage of participants by Anatomical Therapeutic Chemical class (ATC level 2) and preferred term (ATC level 4).

All “Cognitive enhancers” defined by verbatim terms: donepezil (Aricept, Adlarity), galantamine (Razadyne, Reminyl), rivastigmine (Exelon) and memantine (Namenda, Ebixa, Nemdatine) will be summarized separately. All concomitant medication data will be listed. The cognitive enhancers will be flagged in the concomitant medication listing.

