13.2. Efficacy Data

Table 6: Efficacy Data

Table Number	Population	Table Title/Summary
14.2.1	ITT	Summary of Primary, Secondary, and Exploratory Endpoints-Primary Efficacy model
14.2.2.1.1	ITT	Summary of Change from Baseline to Week 52 in ADAS-Cog12 Total Score by Visit and Treatment
14.2.2.1.2	ITT	Summary of Change from Baseline to Week 52 in ADAS-Cog12 Total Score By Visit and Treatment: Responder Analysis
14.2.2.1.3	ITT	Summary of Change from Baseline to Week 52 in ADAS-Cog12 Total Score By Visit and Treatment: Time Component Test
14.2.2.2	ITT-mild	Summary of Change from Baseline to Week 52 in ADAS-Cog12 Total Score By Visit and Treatment
14.2.2.3	ITT	Summary of Change from Baseline to Week 52 in ADAS-Cog12 Total Score By Visit and Treatment: Imputation Missing Not at Random
14.2.2.4.1	ITT	Summary of Change from Baseline to Week 52 in ADAS-Cog12 Total Score By Visit and Treatment Stratified by Mild (21-27)/Moderate (<21) AD Status
14.2.2.4.2	ITT	Summary of Change from Baseline to Week 52 in ADAS-Cog12 Total Score By Visit and Treatment Stratified by Mild (21-27)/Moderate (<21) AD Status: Responder Analysis
14.2.2.4.3	ITT	Summary of Change from Baseline to Week 52 in ADAS-Cog12 Total Score By Visit and Treatment Stratified by Mild (21-27)/Moderate (<21) AD Status: Time Component Test
14.2.2.5.1	ITT	Summary of Change from Baseline to Week 52 in ADAS-Cog12 Total Score By Visit and Treatment Stratified by Mild (20-27)/Moderate (<20) AD Status
14.2.2.5.2	ITT	Summary of Change from Baseline to Week 52 in ADAS-Cog12 Total Score By Visit and Treatment Stratified by Mild (20-27)/Moderate (<20) AD Status : Responder Analysis
14.2.2.6	ITT	Summary of Change from Baseline to Week 52 in ADAS-Cog12 Total Score By Visit and Treatment Stratified by Age
14.2.2.7	ITT	Summary of Change from Baseline to Week 52 in ADAS-Cog12 Total Score By Visit and Treatment Stratified by Gender
14.2.2.8	ITT	Summary of Change from Baseline to Week 52 in ADAS-Cog12 Total Score By Visit and Treatment Stratified by Ethnicity
14.2.2.9	ITT	Summary of Change from Baseline to Week 52 in ADAS-Cog12 Total Score By Visit and Treatment Stratified by Race

Table Number	Population	Table Title/Summary
14.2.2.10	ITT	Summary of Change from Baseline to Week 52 in ADAS-Cog12 Total Score By Visit and Treatment Stratified by ApoE Genotype
14.2.2.11	ITT	Summary of Change from Baseline to Week 52 in ADAS-Cog12 Total Score By Visit and Treatment Stratified by Baseline Cognitive Enhancer Status

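### Cognitive enhancers are flagged from the typed medication text against a fixed name list, although the same records are coded in WHODrug; the coded name is the better basis (minor)

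*SAP*

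**What the plan says.** SAP 7.3 (prior medications) sets cognitive enhancers apart as drugs "defined by verbatim terms: donepezil (Aricept, Adlarity), galantamine (Razadyne, Reminyl), rivastigmine (Exelon) and memantine (Namenda, Ebixa, Nemdatine". SAP 9.6 (concomitant medications) repeats the rule, beginning "defined by verbatim terms: donepezil (Aricept, Adlarity), galantamine (Razadyne, Reminyl", and adds: "The cognitive enhancers will be flagged in the concomitant medication listing". The list has four generic names and eight brand names, with no wording to mark it as a set of examples.

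SAP 6.1.8 provides a coded version of the same records: "Prior and concomitant medications will be classified using Anatomical Therapeutic Chemical class (ATC level 2) and preferred term (ATC level 4", with the dictionary given as "WHODrug Global B3 version March2021".

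SAP 8.4 lists among the efficacy subgroups "medication use (cognitive enhancers, defined as yes or no" and does not refer back to 7.3 or 9.6. In SAP 13.2 the corresponding tables for ADAS-Cog12 (14.2.2.11), ADCS-ADL (14.2.3.11) and iADRS (14.2.4.10) are titled "Stratified by Baseline Cognitive Enhancer Status". Tables 14.3.7.2 and 14.3.7.3 summarise enhancers taken before and after first dose, and listing 16.2.9.3.2 lists them.

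**The concern.** Verbatim text is what a site typed. With participants from about "77 clinical sites in the U.S., Canada and Australia", some entries may be misspelt, abbreviated or given under a name that is not on the list. A closed name list errs mainly in one direction: it can miss a user but will rarely flag a non-user. Coding exists to resolve such variants, and the SAP already requires it, yet the flag is built on the uncoded field.

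Two things are at stake. First, outputs on the same participants could disagree. A record that is coded to donepezil but typed in an unlisted form would appear under its coded term in the general medication table and be absent from the enhancer table, and no rule says which prevails. Second, missed users would sit in the non-user subgroup and pull its estimated treatment effect toward that of users.

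The variable has some weight in this trial. Protocol 6.3 names cholinesterase inhibitors and memantine as examples of drugs that may confound cognitive testing. The primary estimand handles concomitant medication by treatment policy, so the enhancer summaries and this subgroup are where a reader will look for the influence of background therapy.

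**Working it through.** **Planning figures (SAP 2.2), reproduced first because they are used below.** The assumed effect is 45% of 5.0 = 2.25 points, with SD 8.5, two-sided alpha 0.05 and 90% power.

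n per group = 2 × (1.960 + 1.282)² × 8.5² / 2.25² ≈ 300, and 300 / (1 − 0.20) = 375. Both match the plan, and this point does not affect them. Randomised N is 804.

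**Dilution.** Let u be the true share of users and m the share of users whose entry the list misses, with no false positives.

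- Misfiled participants = 804 × u × m.
- Share of true users in the recorded non-user group: c = um / (1 − u + um).
- If missed users respond like other users, the recorded non-user effect is (1 − c) × (non-user effect) + c × (user effect). The user/non-user contrast is therefore multiplied by (1 − c).

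**Assumed values.** The documents give neither u nor m. For u = 0.65 and m = 0.05: 804 × 0.0325 ≈ 26 misfiled, and c = 0.0325 / (0.35 + 0.0325) = 0.085.

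**Comparison with sampling error.** With 300 evaluable per arm and a true split of u to 1 − u, the standard error of the contrast is 8.5 × √(2/(300u) + 2/(300(1 − u))). At u = 0.65 this is 8.5 × √(2/195 + 2/105) = 1.46 points. Suppose the true contrast were as large as the whole planned effect, 2.25 points. The loss is then 0.085 × 2.25 = 0.19 points, or 0.13 standard errors.

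| Users u | Missed m | Misfiled of 804 | c | Contrast kept | Loss if true contrast is 2.25 | SE of contrast | Loss / SE |
|---|---|---|---|---|---|---|---|
| 50% | 2% | 8 | 2.0% | 98.0% | 0.04 | 1.39 | 0.03 |
| 65% | 5% | 26 | 8.5% | 91.5% | 0.19 | 1.46 | 0.13 |
| 80% | 5% | 32 | 16.7% | 83.3% | 0.38 | 1.74 | 0.22 |
| 80% | 10% | 64 | 28.6% | 71.4% | 0.64 | 1.74 | 0.37 |
| 80% | 20% | 129 | 44.4% | 55.6% | 1.00 | 1.74 | 0.58 |

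**Where the flag is not used.** It is absent from the covariates (SAP 6.1.2), the testing hierarchy (6.1.3) and the co-primary model (8.1).

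**The case against.** The strongest reply is that the documents describe no misfiling. They give no matching rule: exact string, partial match and manual review are all possible, and nothing says that an unmatched record becomes a no. The list can be read as naming four drugs, with brands as a help to the programmer. Because the generic names are on it, many entries will match. These drugs also bear on eligibility (inclusion criterion 12, exclusion criteria 29 and 30), so sites have reason to record them with care. The documents show no misspelt entry, unlisted brand or combination product. All of this stands, and it is why the consequence is stated conditionally.

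It also stands that 8.4 does not say which definition it uses. The link to 7.3 and 9.6 is an inference, though no other definition exists.

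A reader might infer that enhancer use will be under-reported throughout. The documents do not support that. The same two sections tabulate all medications by coded term (Tables 14.1.2.4.1.1 and 14.3.7.1) and list every record, so a missed entry would still be visible, only unflagged.

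The reply does not remove the point. If looser matching or manual review is intended, it is an unwritten judgement over a pre-specified subgroup, and the blinded data review in SAP 5 is described only as confirming analysis sets.

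**Conclusion.** The point holds as a minor one. The SAP states a rule on the poorer of two sources that it already has, and defining the flag on coded data would be better at almost no cost.

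The consequence is conditional on three things: the list is applied literally, 8.4 uses this definition, and some users are entered under unlisted text. The size cannot be known from the documents. At 65% use and 5% missed it is about 26 participants and an 8.5% shrinkage of the contrast. Even at 80% use and 20% missed, the loss stays below one standard error of a contrast as large as the planned effect.

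A reader might go further and conclude that the treatment comparison is biased, or that a real subgroup difference would be hidden. Neither follows. Baseline medication entries should be unrelated to randomised arm, so misfiling blurs one contrast in one direction, and sampling error dominates that contrast. No confirmatory result depends on the flag.

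**What to change.** In SAP 7.3 and 9.6, replace the verbatim rule with one on the WHODrug-coded record: any medication coded to donepezil, galantamine, rivastigmine or memantine, alone or in combination, whatever text was entered. Name the coded field to be used (preferred name or substance), because 6.1.8 pairs preferred term with ATC level 4 and does not say that records resolve to the ingredient. Add a blinded review of the resulting list of flagged records before database lock. State in 8.4 that the subgroup uses this flag at baseline, and use the same flag for Tables 14.3.7.2 and 14.3.7.3 and the listings.

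The cost is a short edit in three SAP sections and some programming on data already coded. It needs no new data and does not affect power or the primary analysis.

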7.4. Exposure and Compliance

Study drug exposure and compliance data will be collected in the case report form (CRF).

Study drug exposure data will be summarized as treatment duration (days), study drug exposure (days), and average daily dose (mg/day) by treatment received and overall.

Study drug compliance data will be summarized as total number of planned doses (tablets), total number of doses (tablets) taken, and compliance (%) by treatment received and visit.

Compliance will be summarized as a continuous outcome using mean, SD, median, min, and max, and as a categorical variable. For the categorical analysis, a participant will be considered compliant if the amount of medication taken is within the range of 75% - 125% of the amount of medication planned to be taken.

All study drug administration, accountability and exposure data will be listed.

8. Efficacy Analysis

8.1. Co-Primary Efficacy Analysis

Visit wise mean changes from baseline will be analyzed in the ITT analysis set using a restricted maximum likelihood (REML)-based repeated measures approach (MMRM). The MMRM analysis assumes a missing at random (MAR) missing-data mechanism, meaning that drop out is related to observed outcomes of the dependent variable and covariates, but not to the unobserved outcomes. The analysis will include the categorical, fixed effects of treatment group, visit, and pooled site, along with the continuous, fixed covariates of baseline value of the endpoint being analyzed (baseline), baseline MMSE score, and the interactions of treatment group, baseline, and baseline MMSE with visit. An unstructured (co)variance structure will be used to model the within-participant errors. If this analysis fails to converge, the following structures will be tested in this order, with the first structure yielding convergence to be used as the appropriate structure for that variable: heterogeneous Toeplitz, heterogeneous compound symmetric, and compound symmetric. If one of the structures other than unstructured is used, variance of the Maximum Likelihood Estimator (MLE) will be based on the Sandwich Estimator (empirical option in PROC MIXED statement). If none of the structures yield convergence, site will be removed from the model and the sequence of covariance structures will be refit as described above. The Kenward-Roger approximation will be used to estimate denominator degrees of freedom.

Significance tests for the between-treatment group differences will use a two-sided 0.05 level, with the primary analysis based on the ITT analysis set.

8.1.1. Sensitivity Analyses of the Primary Efficacy Endpoint

A missing not at random (MNAR)-based copy reference approach will be used as a sensitivity analysis to assess robustness of inferences on the co-primary analyses to departures from MAR. Mean changes from baseline in the co-primary endpoints will be analyzed based on data observed while the participants remain on study as well as data imputed using multiple imputation for time points at which no value is observed.

Imputation of values in the reference (placebo) arm will assume MAR. Imputation of values in the active arm will be based on the imputation model for the placebo group, thereby imputing placebo-like values for drug group dropouts. This approach assumes any benefit from the active treatment diminishes over time in accordance with the correlations between repeated measurements.

Intermittent (non-monotone) missing data will be imputed first based on MCMC. An example code fragment is included below. YOBS1-5 are the five postbaseline values of the endpoint being imputed.

```
PROC MI DATA = XXX OUT = YYY_MIOUT NIMPUTE=200 SEED=123;
  BY TRT;
  MCMC IMPUTE = MONOTONE;
  VAR BASELINE MMSE_BASELINE YOBS1 YOBS2 YOBS3 YOBS4 YOBS5;
RUN;
```

The remaining monotone missing data for all participants who discontinue study prematurely will be imputed using a sequential regression multiple imputation model based on data from the

reference arm (placebo) only. Missing values in the placebo and active arms will be imputed from the imputation model developed from the placebo arm. No rounding or range restrictions will be applied to imputed continuous values.

Example code to implement this analysis is listed below.

```
PROC MI DATA=YYY_MIOUT SEED=1214 OUT=YYY_MIOUT2 round=1 NIMPUTE=200;
  CLASS TRT;
  MONOTONE METHOD=REG;
  VAR BASELINE MMSE BASELINE YOBS1 YOBS2 YOBS3 YOBS4 YOBS5;
  MNAR MODEL (Y1 / modelobs=(trt'1'));
  MNAR MODEL (Y2 / modelobs=(trt'1'));
  MNAR MODEL (Y3 / modelobs=(trt'1'));
  MNAR MODEL (Y4 / modelobs=(trt'1'));
  MNAR MODEL (Y5 / modelobs=(trt'1'));
Run;
```

Results from analyses of the multiply imputed data sets Will be combined using Rubin's rules as implemented in PROC MI Analyze.

To assess sensitivity of inferences to handling of the intercurrent event of death, the following approach will be used. Missing data resulting from patient death will be imputed using the worst observed result at each respective visit. The primary analysis as described above will be applied to this data set. At the time of SAP finalization, only four patients had died. Therefore, how this ICE is handled is unlikely to appreciably influence results.

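### The example code for the copy-reference sensitivity analysis (SAP 8.1.1) does not carry out the two-stage imputation that its own text describes

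*SAP*

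**What the plan says.** SAP 8.1.1 describes the copy-reference analysis in prose and in two code blocks, introduced by "An example code fragment is included below" and "Example code to implement this analysis is listed below".

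- **Stage one** fills intermittent gaps by MCMC within treatment arm: "PROC MI DATA = XXX OUT = YYY_MIOUT NIMPUTE=200 SEED=123".
- **Stage two, prose:** "The remaining monotone missing data for all participants who discontinue study prematurely will be imputed using a sequential regression multiple imputation model", fitted to placebo data and used for both arms. The text adds: "No rounding or range restrictions will be applied to imputed continuous values". It names the five post-baseline values YOBS1 to YOBS5.
- **Stage two, code:** "PROC MI DATA=YYY_MIOUT SEED=1214 OUT=YYY_MIOUT2 round=1 NIMPUTE=200". There is no BY statement. The VAR list holds YOBS1 to YOBS5, but the five MNAR statements refer to Y1 to Y5, the first starting "MNAR MODEL (Y1 / modelobs". The reference arm is TRT level 1, and the section does not say that this is placebo.
- **Pooling:** "Results from analyses of the multiply imputed data sets Will be combined using" Rubin's rules.

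Nothing in the SAP says that stage two runs once inside each stage-one data set, or which model is fitted to the completed sets. The integer rounding in SAP 6.1.4 concerns missing ADAS-Cog12 items and does not explain the rounding option here.

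**The concern.** In a two-stage imputation, each stage-one data set should be completed once, giving 200 complete trials to analyse and pool. The printed code instead treats the stacked file as one large trial and imputes it 200 times. Each output set then holds every participant 200 times, and Rubin's rules no longer apply as intended.

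The Y1–Y5 mismatch matters for another reason: the MNAR statements are what make this a copy-reference analysis. If they were dropped so that the step ran, it would become a missing-at-random imputation pooled over both arms.

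This is the only check of the missing-at-random assumption that covers all dropouts, and it feeds Tables 14.2.2.3 and 14.2.3.3. The other check in SAP 8.1.1 covers deaths only. There were four at SAP finalization, against about 160 dropouts if the planning rate applies (20% of 804). Because the code has to be edited before use, whoever edits it decides how the copies are handled, and so sets the standard error and p-value.

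**Working it through.** **Background.** SAP 2.2 gives a placebo change of 5.0, SD 8.5, a 45% difference, two-sided 0.05 and 90% power. The difference is 0.45 × 5.0 = 2.25. Then n = 2 × (1.960 + 1.282)² × 8.5² / 2.25² ≈ 300 per arm, and 300 / 0.80 = 375. The plan's sample size reproduces and is not in question.

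**Record counts.** Inputs are 804 randomized (SAP 2.2) and `NIMPUTE=200` in both stages (SAP 8.1.1). The stage-two counts assume the MNAR names have been corrected so that it runs.

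- Stage-one output: 200 × 804 = 160,800 rows.
- Stage two as printed: 200 × 160,800 = 32,160,000 rows, or 40,000 per participant.
- Stage two as intended: 160,800 rows, or 200 per participant.

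**Effect on the standard error.** This was simulated in Python; no SAS was run. Assumptions not in the SAP are 402 per arm, AR(1) correlation between visits, visit SDs rising from 4.5 to 8.5, and monotone dropout with equal hazard at each visit. There were no intermittent gaps, so the stage-one copies are identical. Week 52 was analysed by ANCOVA on treatment, baseline and MMSE. On complete data this matched an unstructured-covariance model with every covariate by visit (both −1.9046, SE 0.6057), so it stands in for the Section 8.1 model without site.

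Null case, 20% dropout (1,000, 2,000, 2,000 and 1,000 trials by row):

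| Correlation | Intended Rubin SE | Copies separated | Copies clustered on participant | Empirical SD of intended estimate | Rejection: intended / separated / clustered |
|---|---|---|---|---|---|
| 0.4 | 0.659 | 0.653 | 0.538 | 0.544 | 1.3 / 1.3 / 5.3% |
| 0.6 | 0.655 | 0.650 | 0.543 | 0.555 | 2.7 / 2.6 / 5.8% |
| 0.8 | 0.644 | 0.641 | 0.555 | 0.536 | 1.8 / 1.8 / 4.2% |
| 0.9 | 0.633 | 0.631 | 0.567 | 0.584 | 2.6 / 2.6 / 5.2% |

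- **Separated into 804-row sets:** SE 0.3% (0.631 against 0.633) to 0.9% (0.653 against 0.659) lower.
- **Clustered on participant:** over single trials, the intended SE is 1.09 to 1.27 times the clustered SE at 20% dropout, and 1.04 to 1.41 times over 10–30%.
- **All rows treated as independent:** SE 13.4 to 14.9 times too small (√200 = 14.1), with null rejection of 87–89%.
- **Planned effect** (500 trials each at correlations 0.6 and 0.8): significant in 88.4 and 88.0% as intended, 87.6 and 88.6% separated, and 94.2 and 92.2% clustered.
- **Point estimate:** the means differ by 0.002 points or less between readings. The largest shift in a single trial was 0.053 at 20% dropout and 0.108 at 30%.

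A separate simulation, with dropout depending on the previous score, gave an SE of 0.659 as intended, 0.661 separated and 0.046 with all rows independent. Rounding alone moved the result only from −1.725 (SE 0.659) to −1.723 (SE 0.662), which is negligible.

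**The case against.** The code is labelled as an example, so the prose should govern. The prose does settle the reference arm, the order of the stages, the absence of rounding and the variable names. An error is also unlikely to pass unseen: the step probably fails until edited, and the unstructured model in Section 8.1 presumes one record per participant and visit.

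Of the three readings, separation is harmless. Clustering is not invalid: its SE is close to the true sampling SD and type I error is near 5%, so it gives up the conservatism of the Rubin SE rather than validity. Section 8.1 uses a sandwich variance only if the unstructured fit fails to converge, so clustering is not its default. No passage proposes treating the rows as independent. The SE figures rest on assumptions outside the documents, and with identical stage-one copies they test the link between stages only in its simplest case. Finally, this sensitivity analysis sits outside the hierarchy in SAP 6.1.3.

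All of that stands and limits the weight of the point. It does not supply the missing instruction. The prose nowhere links the two stages, the code is the only description of that link, and the code is wrong.

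**Conclusion.** The concern holds. The mismatches between text and code are plain on the page, and no other section corrects them. The missing `BY _Imputation_` with the repeated `NIMPUTE=200`, and the wrong MNAR names, are substantive. The rounding is a contradiction without practical effect.

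The size of the damage is conditional. It runs from negligible to an SE reduced by a factor of 1.09 to 1.27 (20% dropout, correlation 0.4 to 0.9), with about 14 as a worst case that nobody proposes. How SAS handles an existing `_Imputation_` variable or duplicate participant-visits was not tested. The primary MMRM, the testing hierarchy and the point estimate are essentially untouched. This should be corrected before programming. It is not evidence that the analysis was run wrongly.

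The space in the MMSE baseline name and the missing equals sign in the MNAR statements may come from reading the PDF and are not counted as errors.

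**What to change.** In SAP 8.1.1:

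1. Sort `YYY_MIOUT` by `_Imputation_`, since stage one runs BY TRT.
2. Write stage two as `PROC MI DATA=YYY_MIOUT NIMPUTE=1 SEED=1214 OUT=YYY_MIOUT2; BY _Imputation_;` and keep `CLASS TRT`.
3. Delete `round=1`.
4. Use YOBS1–YOBS5 in the MNAR statements, and confirm that the source file has `MMSE_BASELINE` in the VAR list.
5. State which TRT code is placebo.
6. Add one sentence: the Section 8.1 model is fitted BY `_Imputation_` to each of the 200 completed data sets, and the 200 results are then pooled by Rubin's rules.

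The cost is a few lines of code and one sentence, with no effect on data or timeline.
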